If this is a clinical investigation, list and describe who is sponsoring this study. Please provide addresses for all sponsors. If the sponsor and funding source are the same, please state as such. If you are conducting a clinical investigation, you are required to list and describe who is sponsoring this study. (If the study is not sponsored, then state Not Applicable.)

Same as the funding source.

Conflict of Interest:

Describe any potential or apparent conflict(s) of interest that may exist. (If the study is neither funded nor sponsored, then state *Not Applicable*.)

The investigators do not benefit from the outcomes of the proposed study, except the funding provided by the Sponsor to the Pacific University and eye clinics associated with this study.

Describe any other potential conflict(s) of interest that may exist.

None.

Payment of Research Participants

Will you be paying your research participants? YES NO N/A

Please refer to the Office of Research's website for current practices regarding payment of research participants. You may be required to submit additional documentation to the IRB depending on the source of funding."

Institutional Review Board

[name]
(P) [contact] | (F) [contact] | (E) [contact]
(W) www.pacificu.edu/about-us/offices/institutional-review-board

IRB Submission Guidance Document

Study Title

Ocular Adaptation and Visual Performance for Accommodative Contact Lens

Medical Device | Drug Study | Clinical Investigation

Medical Device Information

1. Are you using a medical device in your study that is not the subject of study? The device must be used in YES NO accordance with its approved indications, with no modifications (on-label use).

2. Are you studying a medical device in your proposal? If the medical device is the object of study, is not being used in accordance with its approved indications, or has not been cleared for marketing, please select YES. (If other medical devices are also being used in the study, please select both options, but provide only the information regarding the medical devices being studied on the *Medical Device Study* form.) YES NO

You are conducting a Medical Device Study. Additional information will be required by the IRB. Please provide all required information on the *Medical Device Study* form. Additionally, please provide labels, informational brochures or documents, and other information pertinent to the device(s) that will (a) aide the IRB in review of your proposal and/or (b) be made available to participants to reference. Upload these documents as a separate resource on IRBNet.

Drug Study Information

Are you conducting a drug study? YES NO

Biologic Information

Are you studying a biologic or other food product for human consumption? YES NO

- Biologic
- Other food product for human consumption

Clinical Investigation

Is this project considered a clinical investigation? YES NO

Clinical Investigation Number
NCT02923232

Consent Forms

I will be collecting signed Informed Consent.

Complete the *Informed Consent*

I will be submitting a Request to Alter or Waive Informed Consent.

Check all that apply:

The documentation of signed informed consent will be waived.

Alteration of informed consent documentation (modified consent documents, online *or* anonymous surveys, for instance).

Request to waive Informed Consent.

Vulnerable and Non-Autonomous Populations

1. Will you be collecting data from (1) children/minors, people who (2) cannot provide their own consent or (3) have a disability or impairment?

YES NO

2. Will you be collecting data from pregnant women? YES NO

For non-autonomous individuals, researchers must first obtain permission from the parent or guardian, then informed assent from the potential participant. Please refer to Informed Consent information on the IRB website for additional information regarding the Consent Process, particularly as it applies to Permission and Assent. Based on the answers to these questions, the appropriate forms have been added to the proposal.

Prisoners

Does your research involve prisoners? YES NO

HIPAA and FERPA

HIPAA

Will your research be using data covered by the HIPAA Privacy Rule? YES NO N/A

FERPA

Will your research be using student education record data protected by FERPA? YES NO N/A

Release Documentation

Participant Contact Information

Will you be collecting participant's contact information? YES NO

Recording Release

Will your research include an Audio Recording? YES NO

Photograph and Video Recording Release

Will your research use photographs or video to collect data? YES NO

International Research and Translations

International Research

Will you be conducting research internationally?

YES NO

Translation

Will any verbal or written communication with participants be conducted in a language other than English? YES NO

Recruitment and Data Collection

Recruitment

Will you be recruiting participants for your research? YES NO

- 1) Please place all recruitment materials in one document, as possible, and upload separately on IRBNet.
- 2) List all recruitment materials that will be attached. Recruitment materials include but are not limited to emails, phone scripts, announcement scripts, posters, handouts, and flyers. You may also include text of emails, verbal scripts, etc. in the recruiting section of the proposal if more appropriate. Please do still indicate recruitment elements below, regardless of submission format.
 - Phone-Call Script
 - Announcement Script
 - Email text
 - Poster
 - Handout
 - Flyer
 - Other (if other, please list all other forms of recruitment below)

Data Collection

1) Place all data collection materials in one document, when appropriate, and upload separately on IRBNet. PDFs of online surveys may be uploaded in a second document, as needed.

2) List all Data Collection materials. Data Collection materials include but are not limited to surveys, handouts, demographic forms, assessment tools, and interview questions.

- Assessment Tools
- Demographic Forms
- Interview Questions
- Handouts
- Online Survey:

Please provide the survey's URL:

Please also provide a PDF of the survey as a separate upload.

- Surveys (paper) - Please upload as a separate document.
- Other (if other, please list all other forms of data collection below)

Institutional Review Board

[name]
(P) [contact] | (F) [contact] | (E) [contact]
(W) www.pacificu.edu/about-us/offices/institutional-review-board

Proposal to Conduct Human Subjects Research

Study Title

Ocular Adaptation and Visual Performance for Accommodative Contact Lens

Research Personnel

Investigator(s)

[name], [name], [name], [name] and [name]

Faculty Investigator (required for student investigator research)

Clinical Investigation

Clinical Investigation YES NO

Please provide all Clinical Investigation Information on the *IRB Proposal Guidance Document*.

Purpose

Provide enough relevant information to allow the IRB reviewers to understand the rationale and/or justification for the study and its merits (basic and/or applied), including any relevant study hypotheses and dissemination plans.

Presbyopia is an ocular condition resulting from the reduced flexibility and consequent loss of accommodation, an ability to change the optical power of the human crystalline lens. It results in a limited range of focal distances for forming a clear retinal image. The typical clinical solution to presbyopia is the fitting of single-vision or multifocal spectacle lenses. Alternatively, single- and multi-focal contact lens can be fitted for presbyopes who can adapt to contact lens wearing. Multi-focal lenses provide the convenience of changing focal distances with a single lens; however, unwanted aberrations due to transition between optical zones for different focal distances can be a significant compromise with these solutions.

OneFocus Vision, Inc. (OFV) has previously bench-tested a proprietary design of accommodative contact lens (ACL), and would like to contract the Vision Performance Institute for a non-dispensing (within-laboratory wearing only) clinical test. This novel design of ACL is based on the interaction between the force exerted by the lower eyelid and the fluid (saline or contact lens solution) inside a cavity within the contact lens. The cavity exists within the lens between two layers of hydrogel, and does not get in touch with the corneal surface. The water-absorbing/peameating hydrogel also allows the cavity to be filled with fluid. When the lens is stored in saline or in lens care solution, the cavity will be filled with saline or lens care solution respectively. When it is taken out of the storage box and worn over the eye during the testing, the saline or lens care solution should mostly remain in the cavity, and some (if any) tears might be absorbed into the cavity. OFV bench tests have shown that when micro-pressure (from the lower lid) is applied to the surface above the reservoir(s) containing the fluid, the fluid is pushed through channel(s) and enters a large reservoir extending throughout the optical zone that covers the pupil. Such action in turn changes the optical power of the contact lens that covers the pupil of the eye.

OFV would like the Vision Performance Institute (VPI) at Pacific University and the additional sites (hereafter referred to as Salen, San Diego and New York sites or collectively as the "Co-investigational sites") to conduct testing to confirm the functionality of the test lens on voluntary participants, and to measure the visual performance afforded by the test lens. The three sites will hold their own contract with OFV, but that all data will be processed and published through the VPI.

In the proposed non-significant risk study we plan to recruit presbyopes (people who might have a significant loss of their ability to accommodate their crystalline lens in the eye) to wear a test lens and perform typical clinical tests of visual acuity with different luminance levels and viewing distances/angles. FDA approved commercial ophthalmic equipment will be used at these sites to take images of the test lens on the cornea. These are similar to the typical examinations conducted for regular contact lens wearers. Results of this testing will be used to evaluate the efficacy of test lenses and to provide additional information for revision of test lenses. If shown to provide adequate eye comfort and intended vision correction, this lens design has the potential of allowing tens of millions of presbyopes to utilize contact lenses to improve their functional, everyday vision.

Recruitment

1. Describe the Sample Size and relevant demographics.

Sixty four participants will be enrolled into the study. Up to 110 potential participants will be recruited at the four sites and screened to obtain the needed sample size of 64. Participants should be between 40 and 75 years of age. The number of 64 subjects will allow for detection of a .5 Standard Deviation difference in response time and accuracy with 80% statistical power. This number of participant is usually required for a stage 2 clinical study for validating the efficacy of device design. They will be recruited through flyers posted online (websites) and on bulletin boards around the community surrounding the Forest Grove Campus of Pacific University and other associated eye clinics (see included Flyers).

2. Describe and justify the inclusion of any non-autonomous subjects. N/A

3. Eligibility Criteria?

List and describe the key characteristics necessary for participants in the study.

- Be between 40 and 75 years of age.
- Have normal/corrected-to-normal monocular acuity of better than 20/25 for both eyes.
- Have a photopic (with light stimulation) pupil diameter \geq 2.5 mm.
- Willing and able to wear multifocal contact lenses in both eyes.
- Have a current optical prescription (obtained less than 2 years ago).
- Have spherical equivalent correction equal to or higher than -1.00 Diopter and equal to or less than +0.50 Diopter.
- Have cylindrical correction equal to less than 0.50 Diopter.

4. Exclusionary Criteria

List and describe the criteria that would exclude subject participation in the study (e.g., pregnancy, specific medical condition, English language fluency, age, etc.).

- Have no prismatic correction.
- Without any eye infection, inflammation, disease, or abnormality that contraindicates contact lens wear within the past 6 months.
- No clinically significant ocular pathology (e.g., cataract, keratoconus, dry eye, diabetic retinopathy, or age-related macular degeneration)
- Have no photosensitive disorders, including migraine and seizure.
- Have no binocular dysfunction, including amblyopia, strabismus, and other binocular diseases.

5. Recruitment Plan

Participants will be recruited from the general population using separate recruiting flyers for the four sites (see Recruiting Flyers). The flyers will be posted on the bulletin boards at affiliated eye clinics and other public places, including community centers, local restaurants, and coffee shops. Research personnel will request to post flyers from the appropriate individuals at each location. Participants will call one of the four sites nearest to them, as noted on the flyer, to express their interest in the study and inquire about study criteria. An optometrist (Drs. [name] at VPI, [name] in Salem, [name] in San Diego, or [name] in New York) will speak

with the potential participants on the phone to explain the study criteria and to determine if they meet the criteria included on the recruitment flyer. Candidates satisfying the screening criteria will be invited to the first vision exam session and the exam will be scheduled.

At the beginning of the vision exam session, the subject's consent to the study will be obtained first by the optometrist. S/he will then be examined by the optometrist based on the inclusion and exclusion criteria and tested with their habitually-worn spectacle lenses or contact lenses, if any. Those satisfying the criteria will then be formally entered into the second phase of study.

Study Methodology

1. Location of the Study

Four sites will be involved in the study:

1. VPI: The study will be conducted in [name] at the Forest Grove campus. [name] will conduct the vision screening and lens testing.
2. Salem clinic: Testing will be conducted at [name]. [name] will conduct the vision screening and lens testing.
3. San Diego clinic: Testing will be conducted at [name]. [name] will conduct vision screening and lens testing.
4. New York clinic: Testing will be conducted at [name]. [name] will conduct the vision screening and lens testing.

2. Study Materials, Measures, and/or Apparatus to be Applied

- Test lens: Contact lenses manufactured with standard soft contact lens material, hydrogel, will be tested (see Technical Description of Test Lens). Based on the FDA procedure for classifying medical devices, the test lens should have an expected rating as a Class II, 510K device: proposed identifier 886.5925; product code, LPL (see FDA Device Regulation Guidance at <http://www.fda.gov/MedicalDevices/DeviceRegulationandGuidance/GuidanceDocuments/ucm080735.htm>). The test lens' biological compatibility also meets the FDA testing guidance, as demonstrated by the provided ocular irritation and toxicity reports for soft contact lens (see Ocular Irritation and Toxicity Reports)
- Video image of test lens: Infra-red video camera will be used to record the position of test lens in relation to the edge of pupil and lower eyelid.
- Corneal and test lens profile Image: Ocular coherence topography (OCT) will be taken with Zeiss Cirrus OCT (VPI) or similar anterior segment OCT (Co-investigational sites). Corneal and lens topography will be taken with the Medmont Topography System (VPI) or similar corneal topographer (Co-investigational sites) The OCT and topographer data will be used to visualize the position and shape of the test lens relative to the corneal surface.
- Measure of lens refraction power: Shin Nippon SRW-5500 Open Field Autorefractor (VPI) or other clinical autorefractor (Co-investigational sites) will be used to measure the refractive power and pupil size at different distances and downward angles with and without the test lens.
- Visual acuity testing: An M&S visual acuity testing system (VPI) or similar computerized visual acuity testing system (Co-investigational sites) will be used to display high (95%) and low-contrast (10%) Snellen letters at distance (6 meters), intermediate (75 cm) and near (40 cm) testing distances.

3. Procedures

- Telephone Interview

Each participant will first talk to the optometrist who will determine whether they meet the recruiting criteria. If they meet the criteria, an appointment for the vision exam session will be scheduled.

- Visions Exam Session

During the vision exam session, they will first read, question and sign the consent form. They are now formally enrolled in the study and will then be examined by an optometrist (Drs. [name], [name], [name] or [name]). Distant monocular acuity, distance phoria, and accommodative amplitude will be measured. Additional refractive examinations will be conducted to ensure his/her eligibility. The participant will also be screened for any ocular diseases listed in the exclusion criteria. This will take about 45 to 60 minutes. Participants meeting the screening criteria will be invited back for the lens testing session. The second testing session can be scheduled immediately after the vision exam session or on a subsequent date, if it is more convenient for the patient. In the event that the participant chooses to return on a subsequent date, the optometrist will verbally re-consent the participant before the session begins.

- Testing

The formal testing session will last about 2 hours. At the beginning of the session, corneal topography will be taken without the test lens. The participant will then put on the test lens and corneal topography and corneal ocular coherence topography (OCT) will be taken while s/he views with 0, 15, and 25 degrees of downward angle. The viewing angle is enforced with a forehead/chin rest.

In the second task, participants will be asked to view an eye chart with the 3 downward angles (0, 15, and 25 degrees) and 6m, 75cm, and 40cm distances while their optical refraction is measured with a power refractor. The measured results are then compared to the accommodative demand at these 3 distances.

In the third task, eye charts will be presented at the 3 distances and corresponding angles (6 m for 0 degree, 75 cm for 15 degree, 40 cm for 25 degree)

In the fourth task, video images of the ocular surface will be taken while the eye shifts between 0 to 15 and 25 degrees downward angles and during eye blinks. An infra-red video camera will be mounted on a post in front of the measured eye to acquire the eye images at 15 Hz. These are done for both eyes.

At the completion of the fourth task, the test lens will be removed from participant's eyes. A slit lamp exam will be conducted to at the beginning and end of contact lens wearing to ensure there is no damage to the cornea. The test lens will also be inspected to confirm its integrity. An exit survey will then be conducted and documented to ensure there is no unexpected effect or symptoms except those typically observed with the wearing of soft contact lens (see List of Information Shared with the Sponsor). All data will be aggregated at VPI and then shared with the sponsor based on the above list of shared information.

4. Timeline for Recruitment, Data Collection, Analysis, and Dissemination

Recruiting will begin once IRB approval has been obtained. Data collection will begin immediately after IRB approval and continue until December 31, 2018. Data analysis will be completed before September 30, 2019. Findings will be submitted for publication at an optometric conference once data analysis is completed.

After the completion of data collection, a summary of test results and samples of photos and video images will be provided to the sponsor (see List of Information Shared with the Sponsor). Data collected from the three other sites will be sent to Pacific University who will then share them with the sponsor. The summary report will not include any individual data. All individual images and video/photos will be prepared in a way so that they cannot be used to identify the participant from whom they are taken.

Risks

1. Specifically identify and briefly describe the various risks to which participants may be exposed.

Regarding study risk determination, this study is proposed as a non-significant risk study. Safety testing in accordance with FDA testing requirements for a daily wear contact lens indicates the hydrogel material has been deemed as safe for use in human subjects when the lens is to be exposed to patients for daily use. The study is intended as a non-dispensing, feasibility study to evaluate the design of the accommodating contact lens and poses minimal risk to subjects under the conditions of the study.

Possible risks during testing include a minimal level of eye symptoms similar to what the participant would experience in wearing contact lenses. The symptoms include dry eye and general discomfort but will be short term in nature – probably not extending beyond the testing

session. There is minimal risk in exposing the participant to 2 hours of testing.

2. Describe the likelihood of these risks occurring, how they can and will be minimized, and how they will be handled should they occur.

Viewing discomfort can occur due to dry eye and wearing discomfort. Breaks will be scheduled after each of the four tasks to keep these symptoms at a minimal level. If the discomfort reaches a level that interferes with task performance (as reported by the participant), the task will be paused and the test lens taken out. This should allow the symptoms to dissipate. The participant can terminate their participation or is allowed to resume the task only after the symptoms dissipate to a level that is acceptable to the participant and does not interfere with further participation.

Slit lamp examination will be conducted to confirm the health of the eyes after contact lens wear.

3. Describe any element(s) of deception or meaningful withholding of information associated with the study methodology.

There will be no deception or information withholding involved in the study.

4. Describe any treatment alternatives that may be advantageous to subjects, if clinical investigations are involved.

Alternative treatments available to participants include wearing bi-focal or multi-focal spectacle glasses or contact lenses, or not participating in the study.

Adverse Events

How will adverse events be handled and reported?

Development of any unusual or acute eye discomfort should be relieved immediately by pausing the experiment and taking out the test lens. Although none are expected, any unusually severe and long lasting eye discomfort, that cannot be mitigated by pausing the testing, will be noted and reported to the Institutional Review Board on the next business day. Appropriate modification of the testing procedure will be made to reduce such issues and submitted to the IRB before testing of the lenses continues.

Benefit or Compensation

1. Describe the specific unique benefits subjects will realize via their participation in this study, if any.

We expect no direct benefit to the participants.

2. Describe the payment or other reward participants will receive, if any.

All consented participants will be compensated \$50 for the 1-hour vision exam session, and additional \$100 for the 2 hours of lens testing session. They will receive \$50 if they participate in the vision exam session, but are not invited back for the lens testing session. They will need to provide their Social Security number to receive the payment. If they are a Pacific University employee, their payment will be reported to Payroll (depending on the value of the award/prize, it may be taxable).

For those participating at the VPI site, they will be required to complete the Research Participant Payment Form prior to receiving payment for participation. Additional Pacific University policies regarding payment are included on that form. This form is provided for at the end of the consent documentation as a reference for participants. For those participating at the Salem, San Diego and New York sites, the same form and policy documents will also be provided.

Privacy

How will you protect the privacy of your participants?

All recorded images, examination records, and behavioral performance results will be numerically coded and kept in a file cabinet within a room that is always locked when the research personnel is not in it. Only the PI will have access to the file cabinet. Consent forms will be kept separately from study data. All documents collected from the Salem, San Diego and New York sites will be sent to the VPI and stored separated from study data.

Summary report with group data and de-identified images and videos will be provided to the sponsor for the evaluation of test lens.

Confidentiality will be further preserved by coding individual results with numbers and only mean or group data will be presented in the publication of the results. Any images from the study will be rendered in a way so that the participant cannot be identified. Through use of code numbers, the subjects' identities will be shielded from subsequent testing and data report. Study data and consent forms will be maintained securely for three years after the completion of the study or the date of publication on a journal. After the deadline, the date and document will be destroyed.

Informed Consent

1. How will informed consent be obtained and documented?

Describe the consent process for your study.

After the participant is determined to meet the recruiting criteria based on the phone interview, s/he will be invited to participate in the vision exam session. At the beginning of the vision exam session, a brief description of the vision exam procedure and an explanation of the experimental setup for the lens testing session will be given to the participant by an optometrist (Drs. [name], [name], [name] or [name]) using terms appropriate for them to understand. They are encouraged to ask any questions they might have about the study.

The participant will then read, question, and sign the consent form approved by the Institutional Review Board at Pacific University. If the subject agrees to participate, s/he will be given a copy of the consent form for their record.

If results of the vision exam meet all criteria, the participant will be invited to participate in the second (lens testing) session. If the results do not meet the criteria, his/her participation will be terminated and s/he will be compensated for the first hour of participation. An explanation will be given to the participant as why her participation is terminated, and documented on the consent form.

2. How will participant assent be obtained and documented?

Not applicable.

Institutional Review Board

[name]
(P) [contact] | (F) [contact] | (E) [contact]
(W) www.pacificu.edu/about-us/offices/institutional-review-board

Medical Device Study Information

Study Title

Ocular Adaptation and Visual Performance for Accommodative Contact Lens

Research Personnel

Investigator(s)

[name], [name], [name], [name] and [name]

Faculty Investigator (required for student investigator research)

Medical Device Information

This form is to be used if a medical device, or multiple medical devices, is the subject of study in this protocol. If medical devices are being used for their intended and approved purposes and are not the subject of study, please modify your response to the Medical Device Question.

1. Clearance and/or Approval and Use Information

Medical Device #1

Medical Device Name

Accommodative contact lens

PMA Numbers(s) (as applicable)

Not applicable

501(k) Numbers(s) (as applicable)

Not applicable

Additional Information, as needed

Check all that apply. Please attach the product label information, if available, as a separate document on IRBNet (entitled "Product Name" - Label Information).

- This study involves research on a **medical device** that is cleared and/or approved for marketing.
- The **medical device** is being used in accordance with its approved indications, with no modifications (on-label use).
- The **medical device** is not being used in accordance with its approved indications (off-label use).
- This study involves research on a **medical device** that has not been cleared and/or approved for marketing.

2. Investigation Device Exemption (IDE)

Check all that apply.

- This study involves an investigation that is **exempt** from the **IDE** requirements (21 CFR 812.2(c)).
- This study involves an investigation for which an **IDE is** required.
 - IDE** approval has been obtained from the FDA (please submit as separate document).
 - IDE** approval has not been obtained from the FDA.
 - IDE** approval is automatic because the study is determined to be non-significant risk.

3. Significant Risk (SR) or Non-Significant Risk (NSR) Determination

Check all that apply.

- This is a **SR** medical device (21 CFR 812.3(m)) study.
- This is a **NSR** medical device study.
 - A NSR** determination has been obtained from the FDA (please submit as separate document).
 - A NSR** determination has not been obtained from the FDA.

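### The sample size is tied to response time, which no procedure described in the protocol records

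*Protocol*

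**What the plan says.** Protocol, Recruitment, item 1 (sample size): "Sixty four participants will be enrolled into the study", drawn from up to 110 people screened at four sites. The quantitative justification is one sentence: "The number of 64 subjects will allow for detection of a .5 Standard Deviation difference in response time and accuracy" "with 80% statistical power". No alpha, sidedness or comparison is given there.

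Protocol, Study Methodology, item 2 (materials and measures) lists an infra-red camera for lens position, OCT and corneal topography, an autorefractor, and a computerised acuity system. The autorefractor "will be used to measure the refractive power and pupil size at different distances and downward angles with and without the test lens". The acuity system "will be used to display high (95%) and low-contrast (10%) Snellen letters at distance (6 meters), intermediate (75 cm) and near (40 cm) testing distances".

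Protocol, Study Methodology, item 3 (Procedures) describes an eligibility examination and then four tasks with the test lens. The third is the letter-reading task: "In the third task, eye charts will be presented at the 3 distances and corresponding angles". The sentence then lists the pairs of distance and angle. It names no recorded variable and has no closing full stop.

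**The concern.** A power statement tells the reader which difference the trial can detect, and in which measurement. Here one of the two named measurements has no described source. If response time is wanted, the four sites have no instruction to record it, and it cannot be reconstructed after a single testing session of about two hours. If it is not wanted, half of the sample-size statement describes an outcome outside the trial. Meanwhile refraction, which bears directly on whether the lens changes power, has no stated detectable difference. Acuity has one only if accuracy is read to mean it.

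This is not a detail that a protocol may leave to an analysis plan. Such a plan can choose the model, the alpha and the comparison, but it cannot supply a variable that was not collected.

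**Working it through.** **Step 1. Look for a source of response time, section by section.**

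| Place in the protocol | What is recorded | Response timed? |
|---|---|---|
| Recruitment plan; vision exam session | Testing with habitual correction; monocular distance acuity, phoria, accommodative amplitude, refraction, disease screen | Not described |
| Task 1 | Topography and OCT at three gaze angles | Not described |
| Task 2 | Refraction at three angles and three distances, set against accommodative demand | Not described |
| Task 3 | Eye charts at three paired distances and angles; no variable named | Not described |
| Task 4 | Infra-red video at 15 Hz during gaze shifts and blinks | Not described; 15 Hz is the image rate |
| End of session | Slit lamp, lens inspection, exit survey | Not described |
| Apparatus: acuity system | Displays letters at two contrasts and three distances | Not described |

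Response time has no described source. Accuracy has a plausible one: letters read correctly in task 3.

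**Step 2. Reproduce the protocol's figure.** Inputs from the protocol: difference 0.5 SD, power 80%, n = 64. Assumed: two-sided alpha 0.05, so z = 1.960 + 0.842 = 2.802 and z² = 7.85.

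- Two independent groups: n per group = 2 × 7.85 / 0.5² = 62.8, so 63. The exact t-test gives 63.8, so 64 per group, with power 0.801.
- One group, paired, 0.5 SD of the within-person difference: n = 7.85 / 0.5² = 31.4. The exact t-test gives 33.4, so 34.
- One group, paired, 0.5 SD of the raw score with within-person correlation ρ: the effect in SDs of the difference is 0.5 / √(2(1 − ρ)). At ρ = 0 this is 0.354, and n is about 65.

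So 64 reproduces as a per-group number for two groups, and almost exactly as a paired number at zero correlation. The protocol describes no second group, and it has the autorefractor used both with and without the lens. A within-person comparison is therefore the natural reading for a scheduled outcome.

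**Step 3. What 64 people give within person (all 64 contributing both measurements).**

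- Detectable difference at 80% power: 2.802 / √64 = 0.350 SD of the paired difference; exact t-test 0.356, about 0.36.
- Power at 0.5 SD of the paired difference: 0.5 × √64 = 4.0, and Φ(4.0 − 1.96) = 0.979; exact t-test 0.976, about 98%.
- If 0.5 SD refers to the raw score, power depends on ρ:

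| ρ | 0.5 raw SD, in SDs of the difference | Power at n = 64 |
|---|---|---|
| 0 | 0.354 | 0.795 |
| 0.25 | 0.408 | 0.895 |
| 0.50 | 0.500 | 0.976 |
| 0.75 | 0.707 | above 0.999 |

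Exchanging the outcome name while keeping 0.5 SD and 80% would therefore leave a statement that is wrong for most paired readings. The detectable difference has to be restated with the outcome.

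**The case against.** The strongest reply is that the visible text may not be the whole of what is recorded. The third task is where response time and accuracy would naturally arise, and its sentence appears incomplete, whether in the source or through text extraction. The Privacy section refers in general terms to behavioural performance data, alongside images and examination records. The data-collection materials are separate uploads and are not shown, and a computerised acuity system may log times by default. This stands as a limit on certainty. A reader might infer that response-time data cannot be produced, or that none of the four tasks is timed; the documents do not support either statement. What they support is that no described procedure produces such data. The general phrase in the Privacy section names no measure and does not fill the gap.

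It is also fair to say that accuracy is an ordinary word for letters read correctly. A reader might infer that neither sizing outcome is measured; that goes too far, and only the response-time half is without a source.

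Finally, this is a non-dispensing feasibility study, and a standardised difference does not depend on which continuous outcome carries it. That bears on severity and stands: correcting the text need not alter the number of participants. It does not settle which measurement the stated power describes.

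**Conclusion.** The point holds in limited form. One of the two outcomes named in the only power statement is not produced by any described session, task or instrument. The other is undefined, with a plausible source in the eye-chart task. Severity is moderate.

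A reader might go on to infer that 64 is too few. The documents do not show this. For a within-person outcome, 64 participants reach 80% power at about 0.36 SD of the paired difference and have about 98% power at 0.5 SD. Those figures assume two-sided alpha 0.05, a single comparison, and both measurements from all 64. The protocol states neither alpha nor a dropout allowance.

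**What to change.** Choose one of two amendments.

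(a) If response time is wanted: complete the third-task description under Procedures to say that the computerised acuity system records the time and correctness of each letter response at all four sites. This also defines accuracy. The cost is a common logging setting across acuity systems that may differ between sites.

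(b) If it is not wanted: remove response time from the sample-size statement and tie that statement to an outcome the schedule measures, for example task-two refraction or task-three acuity. Name the comparison (which two conditions, within person or not), give alpha, and restate the detectable difference. For a within-person comparison at two-sided alpha 0.05 the wording could be: 64 participants give 80% power for a difference of about 0.36 SD of the paired difference. The cost is a short amendment and a restated figure, with no added participant burden and no change to 64.
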